3. [name] [name], Akademiskt Primärvårdscentrum in Stockholm, Region Stockholm and Karolinska Institutet, Stockholm, Sweden. Email: [contact]

Investigational sites:

1. Boxholm Vårdcentral, Region Östergötland, Sweden. [name] ([contact])
2. Styrsö Vårdcentral, Västra götalandsregionen, Sweden. [name] ([contact])
3. Lung- och allergimottagningen, Akademiska sjukhuset Uppsala, Region Uppsala, Sweden. [name] [name], professor at Department of Medical Sciences Respiratory, Allergy and Sleep Research ([contact])

Manufacturer of the investigational device, version 5.4.13.5, for education and training of inhalation technique connected to AsthmaTuner system is Medituner AB (org nr:556982-8295), [name], Stockholm. Contact: [contact]

CRO: Karolinska Trial Alliance support. Visit address: Karolinska University Hospital in Solna, Princeton, [name], Stockholm. Contact: [name], [contact]

Expert panel:

The panel supports the clinical investigational trial with expertise on the conception, design, conduction and translation of results of the clinical investigation:

1. [name] and professor in healthcare sciences of asthma and allergic diseases at Department of Södersjukhuset, Karolinska Institutet: Email: [contact]
2. [name] and PhD, Oslo Sports Trauma Research Center, Department of Sports Medicine, Norwegian School of Sport Science, Oslo, Norway. Email: [contact]

A.1.5 Overall synopsis of the clinical investigation

Primary aim: To investigate if app-based education and training of inhalation technique improves the rate of successful inhalation techniques compared with control group at 6-12 weeks follow-up visit.

Secondary aims: To evaluate the feasibility, usability, and safety of the investigational during the study period.

Study design: Two-armed, parallel-designed, individual single-blinded stratified randomisation by inhaler (DPI/MDI/both DPI and MDI) controlled trial with assignment (1:1) to (1) standard care and app-based education and training of inhalation technique or (2) standard education of inhalation technique over 6-12 weeks.

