11	For Handyhaler or similar, check powder drug rests in capsule, if necessary, inhale again	Breathed out and away from the mouthpiece of the inhaler

Each subject in both intervention and control arm will receive standard assessment and instruction on inhalation technique according to criteria in Table 2 at baseline visit. The study endpoints will be collected at the follow-up visit (6-12 weeks).

Randomisation and masking

Each of the 80 subjects is stratified to block of 4 numbers according daily used inhaler of (1) DPI, (2) MDI or (3) both MDI/DPI. Simple randomisation (1 to 1) will be applied in each block and at each study site. The randomisation will be blinded for the evaluator at 6-12 week visit, which practically means that not the same study personnel will do the baseline randomisation and the final 6-12 weeks assessment of inhalation technique.

Endpoints

Primary endpoint is number of subjects presenting successful inhalation techniques as defined by objective endpoints divided by:

- DPI: PIF \geq 30 L/Min, time to PIF <0.5 seconds measured with the investigational device.
- MDI: inspiration time (> 3 seconds) and PIF less than 60 L/Min measured with the investigational device.
- Together with subjective critical endpoints at 6–12-week follow-up visit, assessed by study personnel, Table 2.

Secondary endpoints:

- Feasibility and safety of using the investigational device for education and training of inhalation technique based on questionnaire and interviews from subjects and healthcare personnel, Appendix 3.

Study personnel will get access and be trained in methods and procedures for informed consent, randomisation, investigational device, data collection and documentation. The study endpoints will be documented in electronic Case Report Form (CRF) provided by Karolinska Institutet. Data analysis will start as soon as all 80 included subjects have completed or considered to be lost to follow-up at 6-12 week's visit by local investigator.

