This RCT with multiple investigational sites consists of both primary and secondary level of asthma and COPD care to enabling generalizability of the results and implementation of the investigational device in different healthcare settings. Each study site has one local PI who is responsible for implementing and carry through the investigation. The local study team consist of experienced medical doctors and respiratory nurses in the field, who will receive support, training, and coordination in study procedures from the [name]'s research group at KI. The KI research group will ensure the implementation and progress of the study follow the time plan, but also transparency, streamline the collaboration and find local solution that can prevent occurrence of problems. The study sites will be monitored by Karolinska Trial Alliance (KTA) to ensure compliance with study protocol, safety rules and securing the integrity of subjects. KTA will also train and educate study personnel in Good Clinical Practice (GCP).

Completion of study will be done after subjects have completed the 6-12 weeks follow-up visit, but not later than 12 weeks. Subjects who do not attend the follow-up visit within specified timepoint will be lost to follow-up, not replaced and withdrawn from the primary analysis. Information about feasibility and safety (secondary endpoints) will be collected by healthcare personnel at the

investigational sites after 12 weeks if the study subject has used the investigational device. The investigational device will be removed from the AsthmaTuner app after study completion by [name] research group at Karolinska Institutet. The stratified block randomisation 1:1 between intervention and control arm per study site will ensure the reliability and validity of study results by eliminating selection bias, balance confounding variables.

A.6.2 Investigational device and comparator

Investigational device:

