Subjects lost to follow-up will not be replaced but the decision will be documented in the medical record. Subjects who not attend the follow-up visit 12 weeks after the baseline visit will be categorised as lost to follow-up. They will be asked through email, phone or letter to send in the medical device to the study centre with envelope they received when they received the device at baseline visit. Study sites will be informed about which subjects were lost to follow-up.

Point of enrolment and randomisation

At least 80 subjects will be invited to participate in the investigation, through phone, digital meeting (Teams or Zoom or similar) or at physical at the baseline visit. The study personnel at investigational site will contact the study centre through phone to receive the randomisation assignment and study ID. The anticipated distribution is a minimum of 10 subjects per each participating investigational site.

Expected duration of each subject's participation is 6-12 weeks after enrolment to the investigation. The follow-up visit will be booked 6 weeks after study enrolment but no longer than 12 weeks. Subjects unable to attend the 6-12-week follow-up visit will be withdrawn from the primary analysis of study. The number of subjects required to be included in the investigation is estimated on background of power calculation (see section A7). The timeline is to enrol subject to the investigation during the fall of 2024 and spring of 2025. No additional care is required after the investigation beyond what was initially planned for each subject.

Target and vulnerable populations

The target population for the medical device are patient treated for asthma or COPD or any other disorder requiring treatment with DPI or MDI in primary or secondary care setting. However, neither patient with other diagnosis or children under the age of 16 years will not be included in the study. Although schoolchildren below the age of 16 are considered as target populations for the medical device, we consider we have sufficient data from this population from the pilot study (Appendix 4). Vulnerable, pregnant and breastfeeding population fulfilling the inclusion criteria are welcome to participate, no adverse effects or events are expected in this vulnerable population as longs they will be able to attend the follow-up visit.

A.6.4 Procedures

The subjects will undergo the following procedures as summarized in Table 3.

Procedures	Baseline visit	6–12-week follow-up visit

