Informed consent	X	
Randomization	X	
Questionnaires of medical history and usability	X	X
Spirometry test	X	
Standard review and correction of inhalation technique	X	X
Objective assessment of inhalation technique		X
Adverse events or device deficiency		X

Randomisation

Computer-based randomisation stratified for subjects' daily inhaler use into three groups of DPI, MDI or both DPI and MDI devices of four block numbers in each stratum per investigational site.

Interview and electronic questionnaires

- A structured health questionnaire completed at the first visit will provide information regarding medical history, health care utilization and experiences of inhalation education and training, Appendix 4.

Dynamic spirometry

- The lung function test will measure forced expiratory flow in one second (FEV₁), forced vital capacity (FVC), and FEV₁/FVC according standardised procedures [31]. Applied percent of predicted reference values, adjusting for age, sex, height, weight and ethnicity, will be calculated based on continuous prediction equations of normal population [32].

Standard review of inhalation technique

- All subject's ability to handle their inhaler(s) and inhalation technique will be reviewed and corrected at baseline visit and assessed at 6–12-week follow-up visit according to endpoints in Table 2.

Investigational device - app-based intervention for education and training of inhalation technique

1. Subjects randomised to intervention will receive instructions on using the investigational device, accompanied with written information (instructions for use) from study personnel at baseline visit. The subjects are instructed to use the investigational device 3-7 times per week to achieve the maximal effect.

2. Instruction for use manual on how to use medical investigational device will be available for subjects and study personnel at investigational sites (Appendix 5). Briefly, subjects follow the following procedure:
 - a. Baseline visit: Download (Apple Store or Google Play) and login with BankID or similar to the AsthmaTuner app. Automatic Bluetooth connection will be established between the MIR AsthmaTuner and the app.
 - b. Study personnel at Karolinska institutet set up login through BankID or SITHS card to AsthmaTuner Careportal for study personnel at investigational site.
 - c. Enter patient information: Fill out patient's initial letters, study ID, height, weight and type of inhaler. Press "next" to start the test.

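### A stated, fixed block size of 4 within site and inhaler stratum could let unmasked site staff know up to about 29% of allocations in advance, so the claim that selection bias is eliminated is too strong

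*Protocol*

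**What the plan says.** **Block size.** A.6.1 (Randomisation and masking) states: "Each of the 80 subjects is stratified to block of 4 numbers according daily used inhaler". A.6.4 (Randomisation) describes a computer-based list with three inhaler strata and "of four block numbers in each stratum per investigational site". No other size appears, and nothing says the size is varied or kept from the sites.

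**Method within blocks.** A.6.1 adds: "Simple randomisation (1 to 1) will be applied in each block and at each study site". The end of A.6.1 General calls the scheme stratified block randomisation, 1:1 per site.

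**Who learns the assignment.** A.6.3 (Point of enrolment and randomisation) states: "The study personnel at investigational site will contact the study centre through phone to receive the randomisation assignment and study ID". A.6.1 has study personnel trained in the randomisation procedure. A.6.4 has them instruct intervention subjects on the device at baseline. A.8 says subjects cannot be blinded. The masking in A.6.1 covers the evaluator at the 6–12 week visit. A.16 says the allocation must not be disclosed to physicians and investigators, but sends an investigator who needs to unblind to the patient or the study nurse.

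**The claim.** A.6.1 General says the scheme secures reliable and valid results "by eliminating selection bias, balance confounding variables".

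**The concern.** In a balanced block of 4, once one arm has used its two places, the rest of the block is known. Because blocks run within site and inhaler stratum, a site's own staff see every earlier assignment that matters. They need only the block size, which the plan prints, and a tally.

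Someone who knows the next arm can bring an enrolment forward or hold it back. A.13 lets subjects be approached by their own nurse, a study nurse or a doctor, who may already have an impression of their technique. A.15 allows from a few minutes to 1–2 weeks for considering participation, so the timing of enrolment is flexible. Masking the follow-up evaluator protects the assessment; it does not protect the choice of who enters which arm.

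A.6.1 calls the trial confirmatory and A.5 intends it to support a superiority claim. The allocation scheme should therefore not be credited with more than it delivers.

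**Working it through.** The plan gives no figure for predictability, so there is none to reproduce.

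**Inputs**
- Block size 4, allocation 1:1 (A.6.1, A.6.4).
- 80 subjects: "Data analysis will start as soon as all 80 included subjects have completed or considered to be lost to follow-up" (A.6.1).
- Three inhaler strata (A.6.1) and three sites, the last being "3. Lung- och allergimottagningen, Akademiska sjukhuset Uppsala, Region Uppsala, Sweden" (A.1.4). This gives 3 × 3 = 9 cells, averaging 80/9 = 8.9 subjects.
- Site minimum: "The anticipated distribution is a minimum of 10 subjects per each participating investigational site" (A.6.3). At most 80/10 = 8 sites are possible, or 8 × 3 = 24 cells.
- Assumption: staff know the block size and track every earlier assignment in their own cell.

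**1. Complete block of 4.** There are 6 equally likely balanced sequences.

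| Position | Chance the arm is certain | Chance of a correct best guess |
|---|---|---|
| 1 | 0 | 1/2 |
| 2 | 0 | 2/3 |
| 3 | 1/3 | 1/3 × 1 + 2/3 × 1/2 = 2/3 |
| 4 | 1 | 1 |

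Certain share = (0 + 0 + 1/3 + 1)/4 = **33.3%**. Correct-guess rate = (1/2 + 2/3 + 2/3 + 1)/4 = 17/24 = **70.8%**, against 50% by chance.

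**2. Allowing for unfinished blocks.** A cell ending with 0, 1, 2 or 3 subjects in its last block falls short of one third of its size by 0, 1/3, 2/3 or 2/3 certain allocations. If the four endings are about equally likely, the mean loss is (0 + 1/3 + 2/3 + 2/3)/4 = 5/12 per cell. The expected number certain is then 80/3 − (cells × 5/12).

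| Sites | Cells | Expected number certain | Share of 80 | Simulated share |
|---|---|---|---|---|
| 3 | 9 | 26.67 − 3.75 = 22.9 | 28.6% | 28.6% |
| 4 | 12 | 26.67 − 5.00 = 21.7 | 27.1% | 27% |
| 5 | 15 | 26.67 − 6.25 = 20.4 | 25.5% | 25% |
| 8 | 24 | 26.67 − 10.00 = 16.7 | 20.8% | 20–22% |

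The simulation spread 80 subjects at random over the cells with assumed inhaler mixes (equal, 60/20/20, 70/15/15). The mix hardly mattered.

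**3. With varying block sizes.** Simulated for cells of 9 and 27 subjects. Staff are assumed to know the set of sizes but not their order, and to guess optimally.

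| Block sizes | Certain share | Correct-guess rate |
|---|---|---|
| 4 only | 30–31% | 69–70% |
| 4, 6 | about 6% | 66–68% |
| 2, 4, 6 | 3–4% | 67–69% |
| 4, 6, 8 | 2–3% | 65–67% |

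Varying the size removes most of the certainty. It leaves most of the ability to guess.

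**4. The simple-randomisation wording.** Independent 1:1 draws would give a 2:2 split in a group of four with probability 6/16 = 37.5%. That is not block randomisation, so the sentence in A.6.1 conflicts with A.6.1 General and A.6.4.

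**The case against.** Several points on the other side have weight.

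- **One third is a ceiling.** A reader might infer that a third of this trial's allocations can be foreseen. That holds only for complete blocks; with the three listed sites the figure is about 29%, and it requires staff to know the size and keep track. This stands.
- **Recruiter and caller may differ.** A reader might infer that everyone who recruits learns every assignment. The protocol does not say so: A.13 allows several roles to approach subjects, and A.16 tells staff not to disclose allocation to physicians and investigators. But study personnel at the site obtain and deliver the assignment, and A.16 itself presumes that the study nurse and the patient know it. The instruction narrows who knows; it does not prevent the deduction.
- **Steering is indirect.** Consent precedes randomisation. Table 3 schedules the objective assessment, part of the primary endpoint, only at follow-up, so staff could steer only on a general impression or prior acquaintance. This stands. It also means that a resulting baseline imbalance in the objective measures could not be checked.
- **The simple-randomisation wording adds nothing.** Read literally it would remove predictability, because there would be no balanced blocks. It is a separate inconsistency and not further evidence of predictability.
- **The remedy is partial.** The correct-guess rate barely moves. The gain is in allocations known with certainty, which are the ones that make deliberate steering reliable.

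**Conclusion.** The point holds as a design weakness of modest size that should be corrected. The protocol prints a single small block size for each site and stratum, and unmasked site personnel handle every assignment. Up to about 29% of allocations (about 23 of 80) could be known in advance with three sites, and about 20–22% with eight. These are upper bounds that depend on knowledge of the block size and on tracking. The statement in A.6.1 General that selection bias is eliminated is not supported by this scheme.

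A reader might go further and infer that selection bias occurs, or that it has a particular size. The documents support neither: the design permits steering, and nothing shows that it happens. Any size needs an assumed difference in success chance between subjects steered to the two arms, and the protocol gives none. If every certain allocation were steered the same way and that difference were 5 to 20 points, the bias would be 0.286 × 5 = 1.4 to 0.286 × 20 = 5.7 points, against the 25-point difference assumed in A.7. With no steering it is zero.

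**What to change.** 1. In A.6.1 (Randomisation and masking) and A.6.4 (Randomisation), state: *permuted blocks of randomly varying size, 1:1, within site and inhaler stratum; block sizes are held by the study centre and not disclosed to the sites*. Remove the figure 4 from both places.
2. Replace the simple-randomisation sentence in A.6.1 with the same permuted-block wording, so that A.6.1 and A.6.4 agree.
3. At the end of A.6.1 General, claim that the scheme reduces selection bias, not that it eliminates it.

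**Cost.** A regenerated list and a few sentences, with no change to sample size, visits or procedures. Chance imbalance in very small strata rises slightly.

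**Timing.** A.6.3 plans enrolment for autumn 2024 to spring 2025, and the latest revision in A.1.2 is dated 2025-03-13. If enrolment has begun, the new list can apply only to blocks not yet opened, and the change may have to be handled as a modification under A.9. If enrolment is complete, the wording and the claim still need correcting, and the report should state the block size actually used.

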The subjective assessment of inhalation will be conducted ‘blinded’ by study personnel. The assessment will be filmed through Teams or Zoom to facilitate standardised review and judgment of inhalation technique according to Table 2. The film is stored on local hard disk of the computer and will be deleted after the “blinded” assessment is done.

The objective assessment will be performed in both groups according to Figure 3 a-c. Data is stored in the AsthmaTuner cloud.

Compromising factors that might affect the outcomes are i.e. ongoing exacerbation (asthma or COPD), the follow-up visit can therefore be rescheduled within the time frame of 6-12 weeks in case of any medical condition is deemed to affect the study endpoints. The coordinating investigator will

take the decision to withdraw subject in case of any not resolved medical condition, not present at baseline visit, is judged to significantly affect inhalation technique or subject's safety at the follow-up visit.

A.6.5 Monitoring plan

Before the beginning of the investigation, the Sponsor will appoint an independent monitor at Karolinska Trial Alliance (KTA). Monitoring will be performed before, during the study and after the study is completed in accordance with the ISO 14155 GCP (Good Clinical Practice) standard. Study conductance, source data, device accountability, adherence to the study protocol, Good Clinical Practice, and regulatory requirements will be monitored.

Data to be monitored at site are e.g.

- Patient information and Informed Consent. That each patient included in the study has signed an Informed Consent and that no study procedures have begun before the date of the consent.
- That inclusion criteria are met for the included patients
- That all types of adverse events and serious adverse events, device related or not, as well as, those that might have led to SAE shall be reported, and even if those are listed as expected in this Clinical Investigation Plan.
- Check that all CRF data are entered
- Other CRF data will be source data verified against patient records according to a detailed Monitoring Plan (that will contain details regarding the overall monitoring) signed by the Sponsor prior to the start of the study. At least 10% of the patients will have data in the CRFs 100% source data verified.

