The source documents are to be defined at the site before inclusion of the first subject (please see the section below). The investigator must ensure that data is registered and any corrections in the CRF are made as stated in the clinical trial protocol and in accordance with the instructions. The investigator will ensure that the registered data is correct, complete, and that reporting takes place according to the timelines that have been predefined and agreed. The investigator signs the completed CRF. A copy of the completed CRF will be archived at the study site. All changes made to data entered into the eCRF will be recorded in a protected audit trail.

The Data management will be organized locally by data entry personnel and each investigational site. Data will be reviewed by the CRO, Karolinska Trial Alliance (KTA, principal investigator, study Coordinator at the KPE Lung AllergY, QB:84, with further checking and review of clinic records as

necessary. The external monitor will perform source data verification to confirm that data has been entered correctly in the data base.

The cloud based AsthmaTuner system stores information about objective endpoints, is traceable personal ID and labelled with time points, while subjective endpoints are entered directly in CRF sheet and electronic questionnaire through REDCap are stored at Karolinska Institutet. Procedures for data review will be conducted according to standards of GCP. Due to the nature design of the intervention the subjects cannot be blinded. Investigators or study personnel outside the research team will feed data into the computer in separate datasheets so that the researchers can analyse data.

Database cleaning and issuing data queries will be traceable and transparent with logs and data is stored at KI. Audit can be performed at later stage in relation to larger multi-centre study with by certified CRO to assure quality, and to verify the monitoring process and data as appropriate.

Study subject's identity are transcoded and listed in database and in the CRF's. A subject identification list will secure the identity of included patients, the list will be stored in safety deposit at Karolinska Institutet, KPE Lung and Allergy QB:84.

Monitors will on site do monitoring to review the data in the CRFs versus source data and issue queries to the Investigator to correct and clean data before CRF is sent to be entered into the database, stored and kept by the Sponsor.

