To maintain the overall quality and legitimacy of the clinical trial, code breaks should occur only in exceptional circumstances when knowledge of the actual management is absolutely essential for further treatment of the patient. The investigator is encouraged to maintain the blind as far as possible. The actual allocation must NOT be disclosed to physician and investigators, nor should there be any written or verbal disclosure of the management period in any of the corresponding patient documents. The investigator will report all code breaks (with any reason) as they occur on the corresponding CRF and medical record. Unblinding should not necessarily be reason for discontinuation of the trial.

If unblinding is deemed to be necessary, the investigator should ask the patient directly or the study nurse, alternatively contact principal investigator directly on phone number: [name] [name] or [name] [name].

Subjects will continue to receive standard care irrespective of participation or randomization.

A.17 Publication policy

Independently of results of this clinical investigation the result is aimed to be published in academic peer-reviewed journal of high impact. The plan is to publish data within 12 months of end of data collection. The authors will be based on contribution according to standards from international committee of medical journal editors (<http://www.icmje.org>).

The results of clinical investigation will be reported according to ISO 14155:2020, Annex D *Clinical investigation report*, by sponsor within one year after the end of the investigation to MPA.

A.18 Bibliography

1. Jansson, S.A., et al., *The economic consequences of asthma among adults in Sweden*. *Respir Med*, 2007. **101**(11): p. 2263-70.
2. Nordlund, B., et al., The clinical benefit of evaluating health-related quality-of-life in children with problematic severe asthma. *Acta paediatrica*, 2011. **100**(11): p. 1454-60.
3. Vogelmeier, C.F., et al., Global Strategy for the Diagnosis, Management, and Prevention of Chronic Obstructive Lung Disease 2017 Report: GOLD Executive Summary. *Eur Respir J*, 2017. **49**(3).
4. Rabe, K.F., et al., Global strategy for the diagnosis, management, and prevention of chronic obstructive pulmonary disease: GOLD executive summary. *Am J Respir Crit Care Med*, 2007. **176**(6): p. 532-55.

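### The measures stated for blinding the Table 2 rating do not keep the follow-up rater from learning the arm before the rating is fixed

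*Protocol*

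**What the plan says.** **The blind.** A.6.1 (Randomisation and masking) states that the evaluator at the 6–12 week visit is blinded, and explains that this means "not the same study personnel will do the baseline randomisation and the final 6-12 weeks assessment of inhalation technique". A.6.4 (Follow-up visit) says study personnel make the subjective assessment blinded and adds: "The assessment will be filmed through Teams or Zoom to facilitate standardised review and judgment of inhalation technique according to Table 2". The recording is kept on a local computer only until that rating has been made. A.16 forbids disclosing the allocation to physicians and investigators and requires code breaks to be recorded. If unblinding is needed, "the investigator should ask the patient directly or the study nurse".

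**The visit.** Table 3 in A.6.4 places four items at the follow-up visit: "Questionnaires of medical history and usability", the standard review of technique (the Table 2 rating), the objective assessment, and adverse events or device deficiency. On the objective part, A.6.4 says: "The objective assessment will be performed in both groups according to Figure 3 a-c".

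**The subjects.** A.8 states: "Due to the nature design of the intervention the subjects cannot be blinded".

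**The usability data.** A.6.1 says that feasibility and safety information will be collected by healthcare personnel at the "investigational sites after 12 weeks if the study subject has used the investigational device". Table 3 marks usability at the follow-up visit itself.

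**The endpoint.** Under A.6.1 (Endpoints), success requires both the device-measured criteria and the critical steps of Table 2 as assessed by study personnel.

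**The concern.** Using other staff at follow-up removes one route to the allocation, the memory of having randomised the subject. It does nothing about what a new staff member can learn during the visit. The subject knows the arm and nothing in the protocol asks them to keep quiet about it. Answers on the usability of the device, or a report of a device deficiency, can identify an app user.

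This matters because several critical steps in Table 2 are judgements, for example whether a DPI inhalation was forceful or an MDI inhalation slow. One failed critical step makes the subject a failure, so one borderline call can change the primary outcome. A.6.1 calls the trial confirmatory and blinded, and A.5 intends it to support a superiority claim. If the rater knows the arm, the result could be tilted and still be reported as assessor-blinded.

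**Working it through.** **1. Each measure against the routes to the allocation**

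| Measure | What it closes | What it leaves open |
|---|---|---|
| Different staff (A.6.1) | The rater's own knowledge from randomising | Anything learned at the follow-up visit |
| Filming (A.6.4) | Would allow rating away from the visit | No rater without subject contact is named; the film is deleted after rating, so a doubtful rating cannot be reviewed again |
| Non-disclosure rule (A.16) | Deliberate disclosure to physicians and investigators | Subjects are not told to stay silent, and they and the study nurse hold the allocation |

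**2. Each procedure at the visit: can it reveal the arm?**

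- *Usability questionnaire:* yes, directly, if given at the visit. If given only to device users, as A.6.1 implies, handing it out is itself revealing. If it is collected after 12 weeks, as A.6.1 also says, it would generally follow the rating. The two passages do not agree.
- *Device-deficiency record:* yes, where a subject reports a problem with the app.
- *App-based test:* not in itself, because both arms do it. It could reveal the arm indirectly, through familiarity (A.6.4 instructs the app arm to train 3–7 times per week) or stored training data (A.6.4 gives site personnel a Careportal login; A.8 says the cloud data are traceable to a personal ID and time-stamped). This route is inference.

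**3. Order.** Table 3 is a checklist and fixes no sequence. Read as one, it would put the questionnaires before the rating, and the objective test and device deficiencies after it. The A.6.4 text also describes the rating before the objective test. Neither is stated as an order to follow, and no lock of the rating is mentioned.

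**4. Illustration of what is at stake**

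The protocol gives no figure for rating bias, so none can be reproduced. From A.7: 5% significance level, 50% success without the device, 80 subjects in 1:1 allocation, 20% dropout. Evaluable per arm: 40 × (1 − 0.20) = 32. Assumed: no true effect, a two-sided test, and a net bias of 5, 10 or 15 points in the composite. A pooled two-proportion test stands in for the planned logistic regression.

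*Normal approximation*, bias d centred on 50% (p₁ = 0.5 − d/2, p₂ = 0.5 + d/2):

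P(reject) = Φ[(d − 1.96·s₀)/s₁] + Φ[(−d − 1.96·s₀)/s₁], with s₀ = √(2·0.5·0.5/n) and s₁ = √{[p₁(1−p₁) + p₂(1−p₂)]/n}.

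For n = 32 and d = 0.10: s₀ = 0.125 and s₁ = √(0.495/32) = 0.1244. So P = Φ(−1.166) + Φ(−2.774) ≈ 0.122 + 0.003 = 0.125.

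*Exact binomial enumeration* of the same test, with the bias added to the intervention arm only (50% versus 50% + d):

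| Assumed bias | 32 per arm, approx. | 32 per arm, exact | 40 per arm, approx. | 40 per arm, exact |
|---|---|---|---|---|
| 0 | 5.0% | 6.0% | 5.0% | 5.7% |
| 5 points | 6.8% | 8.0% | 7.3% | 8.1% |
| 10 points | 12.5% | 14.2% | 14.4% | 15.7% |
| 15 points | 22.2% | 24.7% | 26.6% | 28.6% |

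The exact column starts at 6.0% with no bias at 32 per arm, so part of the gap between the columns is the test's own size.

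**The case against.** The protocol does more than swap staff. It films the demonstration, so the rating could be made apart from the visit, and A.16 forbids disclosure. Nothing says the Table 2 rater also runs the app test or hands out the questionnaire. Visit order and form locks are often placed in a site manual or CRF instructions, and the CRF (Appendix 7) is not shown. All of this is fair, but the safeguard that the protocol itself states stops short of securing the blind, and filming helps only if the film's rater is kept from the subject and the app data.

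The room for bias is also limited. Some critical steps, such as removing the cap, loading the dose or placing the mouthpiece, are fairly observable. The rating can change the outcome only in subjects who meet the device-measured criteria. If, as an assumption, 70% meet them independently of the rating, a 15-point shift in the composite needs a shift of 15/0.70 ≈ 21 points in the ratings. This stands, and it makes the upper end of the range less likely. Smaller shifts remain plausible.

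A reader might infer that the follow-up procedures do reveal the arm before the rating is made, or that the app test alone unblinds the rater. The documents support neither: the order is unspecified, and the test is done in both groups. Nor do they say that app-arm subjects bring their own device or that the rater sees training history.

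**Conclusion.** The point holds as a weakness of the stated method. Different staff, filming and a general non-disclosure rule leave open routes by which the rater may learn the arm before rating a judgement-based part of the primary composite. It is not shown that this will happen, or in which direction a rater would lean.

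The size is illustrative only. With 50% true success in both arms and 32 evaluable per arm, an assumed bias of 5, 10 or 15 points in the composite gives a false-positive rate of about 6.8–8.0%, 12.5–14.2% or 22.2–24.7%, against a nominal 5% (6.0% exact). These biases have no source in the documents.

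Separately, A.6.1 and Table 3 conflict on when the usability and feasibility data are collected and from whom. The conflict bears on the blind and must be reconciled. Overall this is an inexpensive improvement that should be made; it does not invalidate the design.

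**What to change.** In A.6.4 (Follow-up visit), state that:

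1. Subjects are asked beforehand, and again at the start of the visit, not to mention the app or their allocation.
2. The Table 2 demonstration is filmed, rated and locked in REDCap before the objective test, the usability questionnaire, the device-deficiency record and any return of the device.
3. The rater has no access to AsthmaTuner training data before the lock.

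State also who rates the film. If it is someone who never meets the subject, say so; that would strengthen the blind further. Amend the masking text in A.6.1 to match, and reconcile A.6.1 with Table 3 on the timing of the usability and feasibility data and on which subjects provide them.

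The cost is protocol wording, a form lock in REDCap and a slightly less flexible visit order. Whether a site needs another person to keep the rater separate cannot be judged from the protocol.
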